Patients randomized to the INTELLiVENT-ASV group received this mode of ventilation immediately after the admission in the ICU. Quickwean was immediately activated at that time, but the SBT mode was switch off for the first three hours of mechanical ventilation. It was not possible to extubate the patient without consulting the ICU physician on duty, who made the final call to extubate. Spontaneous breathing trials (SBT) were not applied during the first three hours of mechanical ventilation. The patient was extubated without a SBT if the physicians decided that the patient could be extubated within the first three hours of mechanical ventilation. After the first three hours of ventilation the SBT function

of INTELLiVENT-ASV was initiated and the patient could be extubated if the patient had a successful SBT of at least 10 minutes with a consultation of the ICU physician on duty. The standard operating procedure is described in appendix 2.

In both arms it was possible to deviate from protocol if the ICU physician deemed it necessary for the safety of the patient. In these cases the patient could be switched to the not allocated mode.

In both arms the same alarm settings were used, which were: 1) pressure alarm ≥ 35 cmH₂O; 2) expiratory minute volume alarm ≤ 3.0 and ≥ 15.0 L/min; 3) respiratory rate alarm ≥ 35 breaths per min; 4) tidal volume alarm ≥ 900 ml; 5) apnea time alarm ≥ 30 seconds; 6) EtCO₂ alarm ≤ 30 and ≥ 60 mmHg; and 7) SpO₂ alarm $\leq 90\%$.

Outcomes

Primary outcome:

1. Percentage of time (during at least 30 seconds) in the unacceptable zone according to the total postoperative ventilation time on the ICU during the first three hours of ventilation or until extubation, if extubated earlier.

Secondary outcomes:

1. Percentage of time (during at least 30 seconds) in the optimal and acceptable zone according to the total postoperative ventilation time during the first three hours of ventilation or until extubation, if extubated earlier.
2. Percentage of breaths in the optimal, acceptable and unacceptable zone according to the total number of recorded breaths during the first three hours of ventilation or until extubation, if extubated earlier.

3. Percentage of time (during at least 30 seconds) in the optimal, acceptable and unacceptable zone according to the total number of recorded time.
4. Percentage of breaths in the optimal, acceptable and unacceptable zone according to the total number of recorded breaths.

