19. The number of patients with postoperative pulmonary complications (like pneumonia, pneumothorax, atelectasis on the X-ray within the first 72 hours after surgery).
20. The percentage of breaths that the SpO₂ measurements were $<85\%$ according to the total number of recorded breaths (when the measured SpO₂ had a quality index of $>50\%$).
21. The percentage of breaths that the EtCO₂ and SpO₂ measurements were missing or of a quality of $<51\%$.

22. The median acceptance score (1-10) of the nurse. The answers of the whole survey will be published as supplementary data.

23. During this study the pressure, volume, flow and EtCO₂ wave patterns were recorded to analyze and detect patient-ventilator asynchronies. Currently new algorithms are developed to analyze the wave patterns in an objective and reliable manner. Based on these algorithms the research group will try to compare the number and the type of asynchronies during mechanical controlled and supportive ventilation in both groups. These outcomes will be reported in another manuscript than the outcomes described above.

Study organization

The steering committee was composed of the principal investigator that was also the local coordinating investigator and five experts in ventilator support in critically ill patients all contribute to the design and revisions of the original study protocol and the statistical analysis plan. The local coordinating investigator was responsible for administrative management and for collection and management. The local coordinating investigator was supported by six local investigators to cover in duties when the local coordinating investigator could not record the data. All local investigators were registered in the delegation log. The study was conducted according to the ICH-GCP guidelines, to guaranty integrity of data collection and to ensure timely completion of the case report forms at the bedside completed by the ventilator users.

Data collection

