The ventilatory variables will be extracted from the datalogger output files and transferred to the databases that will be exported for statistical analysis. After that, these study databases will be locked and exported for statistical analysis to the Academic Medical Center, Amsterdam, The Netherlands. The results of this analyses will be documented in a comprehensive database. At this stage, this last database will be locked as soon as all data are entered and all discrepant or missing data are resolved – or if all efforts are employed and remaining issues cannot be fixed. At this step, the data will be reviewed before database locking. At this stage, permission for access to the database will be removed for all investigators, and the database will be archived.

Missing data

No or minimal missing for the primary and secondary outcomes are anticipated, except for the quality and number of SpO₂ measurement in the datalogger. These measurement are assessed with fingertip pulse oximeter that sometimes cannot assess a value or the quality of the assessment is not sufficient. Breaths with missing SpO₂ or a quality of the assessment of < 51% will be excluded from the analyses of the primary and secondary outcomes where this measurements are necessary.

Sample size

A power analysis was performed using G*Power (version 3.1.9.2.; Franz Faul, Universitet Kiel, Duitsland). Based on this analysis the trial was designed to enroll at least 196 patients in total. This number of patients was expected to be sufficient to detect a reduced ventilation time of 14.0 minutes in the unacceptable zone in the INTELLiVENT-ASV group considering a common standard deviation of 10.0 minutes [4], a type I error of 5%, 95% of power, similar allocation of subjects to each group and corrected for dropouts.

Predefined statistical analysis plan

There were no major adjustments from the preliminary analysis plan, as reported previously in the online accessible protocol [1]. In accordance, all statistical analyses will be conducted according to an intention-to-treat principle, considering all patients in the treatment groups to which they were randomly assigned.

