Visual inspection of histograms and D'Agostino–Pearson's normality tests will be used to assess continuous distribution of the data. For the conventional ventilation and INTELLiVENT-ASV arms, the baseline characteristics will be expressed as counts and percentages, means and standard deviations (SD), or medians and interquartile ranges (IQR) whenever appropriate. Hypothesis tests will be two-sided with a significance level of 5%. We will not adjust P -values for multiple comparisons. Analyses will be performed using the R (R Core Team, 2016, Vienna, Austria) program.

Trial profile: Patient flows will be presented in a CONSORT flowchart (Figure 1).

Baseline comparisons: Patient's baseline characteristics will be presented by study arm (eTable 2).

Adherence to study interventions and, ventilator variables and vital signs:

Ventilatory variables and vital signs will be reported from ICU admission until extubation or up to the first 72hours of recorded mechanical ventilation time (eTable 3). These variables, including driving pressure and mechanical power, will be compared among the groups using Student's *t* test. Also, the trend of the ventilator variables every 30 minutes for the first three hours will be compared between the groups using mixed-effect linear models, considering an interaction term between time and group and the patients as random effects.

Outcomes:

Percentage of time in the optimal, acceptable and unacceptable zone for at least 30 seconds during the first three hours of ventilation or until extubation, if extubated earlier, and according to the postoperative total recorded ventilation time (eTable 4).

The number of episodes where the ventilation stays in one of the three zone for at least 30 consecutive seconds will be calculated. Then, this number will be corrected by the total duration of ventilation as:

$$\%_{UZ} = (T_{UZ} / DV) \times 100$$

Where $\%_{UZ}$ is the percentage of time in a zone, T_{UZ} is the time in seconds where the ventilation stays in the specific zone for at least 30 consecutive seconds, and DV is the total duration of ventilation in seconds. This number will be reported as mean \pm standard deviation and median (interquartile range). The effect of the intervention will be estimated with a Student's *t*-test and reported as the mean difference between the two groups. The consistency of the findings of the Student's *t*-test will be tested using a bootstrapped Student's *t*-test with 1,000

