replications. If a very nonsymmetrical distribution is found, we will use the best distribution that fits the data.

Percentage of breaths in the optimal, acceptable and unacceptable zone according to the total number of breaths during the first three hours of ventilation or until extubation, if extubated earlier, and according to the postoperative total recorded ventilation time. (eTable 4).

The percentage of breaths in the three zones will be reported as number and percentages (according to the total number of breaths and not according to the number of patients) and the effects of the intervention will be estimated with risk ratio and 95% confidence intervals calculated with Wald's likelihood ratio approximation test and with χ^2 tests for hypothesis testing.

Number of successful extubations within the first 6, 12 and 24 hours after surgery (eTable 5).

The effects of the intervention on the number of successful extubation within the first 6, 12 and 24 hours of mechanical ventilation after admission on the ICU will be reported as number and percentages and estimated with risk ratio and 95% confidence intervals calculated with Wald's likelihood ratio approximation test and with χ^2 tests for hypothesis testing. These findings will be confirmed using logistic models adjusted by the duration of surgery, total intravenous sedatives dosage and the time from ICU admission until a rectal temperature $>35.5^{\circ}\text{C}$.

Total Time until extubation (considering the time from ICU admission until extubation) (eTable 5).

The time until extubation will be assessed using Kaplan–Meier curves, and hazard ratios with a 95% confidence interval will be calculated with Cox proportional hazard models without adjustment for covariates. The proportional hazard assumptions will be tested and alternative parametric survival models will be used if the proportionality assumption is not sustained. These findings will be confirmed using Cox proportional hazard models adjusted by the duration of surgery, total intravenous sedatives dosage and the time from ICU admission until a rectal temperature $>35.5^{\circ}\text{C}$.

Time until first spontaneous breathing (considering the time from ICU admission until first spontaneous breathing) (eTable 5).

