All recorded time (n/hour) Median (IQR)	Mean ± SD Median (IQR)	Mean ± SD Median (IQR)	Mean difference	Mean ± SD Median (IQR)	Mean ± SD Median (IQR)	Mean difference
Times SpO₂ measurement of <85% during mechanical ventilation*						
First 3 hours (n/3 hours) Median (IQR)	Mean ± SD Median (IQR)	Mean ± SD Median (IQR)	Mean difference	Mean ± SD Median (IQR)	Mean ± SD Median (IQR)	Mean difference
All recorded time (n/hour) Median (IQR)	Mean ± SD Median (IQR)	Mean ± SD Median (IQR)	Mean difference	Mean ± SD Median (IQR)	Mean ± SD Median (IQR)	Mean difference
Lowest measured SpO ₂ over all recorded time.	Mean ± SD Median (IQR)	Mean ± SD Median (IQR)	Mean difference	Mean ± SD Median (IQR)	Mean ± SD Median (IQR)	Mean difference
Missing measurement**: all recorded time EtCO ₂	Mean ± SD Median (IQR)	Mean ± SD Median (IQR)	Mean difference	Mean ± SD Median (IQR)	Mean ± SD Median (IQR)	Mean difference
SpO ₂	Mean ± SD Median (IQR)	Mean ± SD Median (IQR)	Mean difference	Mean ± SD Median (IQR)	Mean ± SD Median (IQR)	Mean difference
Number of interventions						
First 3 hours (n/3 hours) Median (IQR)	Mean ± SD Median (IQR)	Mean ± SD Median (IQR)	Mean difference	Mean ± SD Median (IQR)	Mean ± SD Median (IQR)	Mean difference
All recorded time (n/hour) Median (IQR)	Mean ± SD Median (IQR)	Mean ± SD Median (IQR)	Mean difference	Mean ± SD Median (IQR)	Mean ± SD Median (IQR)	Mean difference
Pulmonary complication (first 72 hours)						
Pneumonia	N / Total (%)	N / Total (%)	Risk ratio	N / Total (%)	N / Total (%)	Risk ratio
Pneumothorax	N / Total (%)	N / Total (%)	Risk ratio	N / Total (%)	N / Total (%)	Risk ratio
Atelectasis	N / Total (%)	N / Total (%)	Risk ratio	N / Total (%)	N / Total (%)	Risk ratio
Overall	N / Total (%)	N / Total (%)	Risk ratio	N / Total (%)	N / Total (%)	Risk ratio
Acceptance score						
Score (1-10) Median (IQR)	Mean ± SD Median (IQR)	Mean ± SD Median (IQR)	Mean difference	Mean ± SD Median (IQR)	Mean ± SD Median (IQR)	Mean difference

*Measurement with a quality index >50%

** Measurement with a quality index <51%

eTable 6 – Intention-to treat analysis and per protocol analysis of the percentage of breaths and time in the optimal, acceptable and unacceptable zones during the first 3 hours of postoperative mechanical ventilation or extubation, and for all recorded breaths for patient who were successfully extubated before or after the median postoperative mechanical ventilation time.

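### Breaths without valid SpO₂ are excluded from the primary analysis while the denominator stays total ventilation time, so applied literally the excluded time counts in no zone

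*Combined protocol and SAP*

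**What the plan says.** The Missing data section expects nearly complete outcome data, "except for the quality and number of SpO₂ measurement in the datalogger". Breaths whose SpO₂ is absent or has a quality below 51% "will be excluded from the analyses of the primary and secondary outcomes where this measurements are necessary". eTable 1 lists SpO₂ with tidal volume, EtCO₂ and peak pressure as the parameters that define the zones.

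Two places fix the denominator of the primary outcome. Under Outcomes, the percentage is taken "according to the total postoperative ventilation time on the ICU during the first three hours of ventilation", or until extubation if that comes first. In the analysis section, the formula is T_UZ / DV × 100, where "DV is the total duration of ventilation in seconds". The numerator counts time in which "the ventilation stays in the specific zone for at least 30 consecutive seconds". The heading of the breath-based zone outcomes likewise sets them against the total number of breaths.

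Signal loss is an outcome in its own right: "The percentage of breaths that the EtCO₂ and SpO₂ measurements were missing or of a quality of" below 51% is secondary outcome 21, and the analysis section compares it between arms. The corresponding row of eTable 5 covers all recorded time and not the three-hour window.

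**The concern.** One section removes breaths from the analysis, and the formula keeps their seconds in DV. Nothing reconciles the two. The plan also does not say when SpO₂ counts as necessary for classifying a breath, or whether an excluded breath interrupts a 30-second run. Two analysts following the plan faithfully could therefore report different primary results from the same datalogger files.

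At stake are the size of the reported difference and, only if loss differs between arms, its direction. Less time in the unacceptable zone is the favourable result, so uncounted time would flatter the arm that loses more signal.

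**Working it through.** **Inputs.** From Sample size: a difference of 14.0 minutes, an SD of 10.0 minutes and 196 patients (98 per arm). From the analysis section: a two-sided 5% test. Assumed, because the documents do not give them: loss rates of 5% to 15%, a 180-minute window behind the 14 and 10 minutes, and loss unrelated to zone.

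**Plan's own figure.** n per arm = 2 × (1.960 + 1.645)² × 10² / 14² = 13.3, so 14 per arm and 28 in total before dropout. The stated 196 is not reproduced. That is a separate matter; here 196 serves only for the standard error: 10 × √(2/98) = 1.429 minutes, so 14 minutes gives z = 9.80.

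**Step 1, the formula as written.** Let V be ventilation time, m the share without valid SpO₂ and u the unacceptable share of valid time. If every breath needs SpO₂, T_UZ = u × V × (1 − m).
- Dividing by V gives u(1 − m), and the three zones together reach at most 1 − m.
- Dividing by valid time, V(1 − m), gives u.
- Example: V = 10,800 s, u = 10%, m = 10%. Unacceptable valid time is 972 s; 972/10,800 = 9.0%, against 972/9,720 = 10.0%.

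**Step 2, when SpO₂ is not needed.** Let f be the share of unacceptable time already unacceptable on tidal volume, EtCO₂ or peak pressure. If those breaths are kept without SpO₂, the result over total time is u[1 − (1 − f)m]. For u = 10%:

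| f | m = 5% | m = 15% |
|---|---|---|
| 0 | 9.5% | 8.5% |
| 0.5 | 9.75% | 9.25% |
| 1 | 10.0% | 10.0% |

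Shrinkage disappears when f = 1. If those breaths are kept but DV otherwise counts only valid time, the error reverses: 10/(100 − 90m) gives 10.47% at m = 5% and 11.56% at m = 15%.

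**Step 3, equal loss in both arms (f = 0).**

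| m | 14(1 − m), min | z | 14(1 − m)/180 | Valid-time DV |
|---|---|---|---|---|
| 0 | 14.0 | 9.80 | 7.78% | 7.78% |
| 5% | 13.3 | 9.31 | 7.39% | 7.78% |
| 10% | 12.6 | 8.82 | 7.00% | 7.78% |
| 15% | 11.9 | 8.33 | 6.61% | 7.78% |

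Here z holds the SD at 10. If the SD shrinks by the same factor, (1 − m) cancels and z stays 9.80. Power exceeds 0.999 either way.

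**Step 4, unequal loss and no true effect (f = 0).** Take 14 unacceptable minutes in both arms, the smallest control value that allows a 14-minute reduction, and keep the SD at 10.
- 5% against 10%: 14 × 0.05 = 0.70 min (0.39 points), z = 0.49, rejection probability 7.8%.
- 5% against 15%: 14 × 0.10 = 1.40 min (0.78 points), z = 0.98, rejection probability 16.5%.

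**Step 5, the 30-second rule.** A simulation assumed 4-second breaths, unacceptable episodes averaging 1 or 3 minutes, a true share of 14/180, loss of 5% to 15% and 300 patients per scenario. The share of the full-data percentage that is kept, with DV on valid time, was:

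| Loss pattern | Any excluded breath ends a run | Gaps up to 8 s do not |
|---|---|---|
| Scattered single breaths | 0.53–0.90 | 0.97–1.00 |
| 32-second blocks | 0.93–0.99 | 0.93–0.99 |
| 2-minute blocks | 0.99–1.00 | 0.99–1.00 |

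With DV as written, 10% loss and runs ended, 0.62–0.67 is kept for scattered loss and 0.90 for 2-minute blocks. For scattered loss, correcting DV alone is therefore not enough.

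**The case against.** The strongest reply is that a breath excluded from an analysis leaves both numerator and denominator, so DV was always meant to be valid time. Secondary outcome 20 points that way, since it attaches an SpO₂ quality condition to a percentage of breaths. This is a possible reading, but the primary formula carries no such condition and its definition of DV says otherwise, so the conflict remains.

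Second, the exclusion applies only where SpO₂ is needed. A breath that is unacceptable on another parameter may not need it, and Step 2 shows that the shrinkage can then be nil. This stands, and it rules out presenting (1 − m) as the plan's result. It also adds another reading that the plan should settle.

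Third, signal loss is already compared by arm. That helps, but the table row does not show it for the primary window.

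Fourth, every loss rate above is assumed, the 8-second gap has no basis in the documents, and with block losses that gap changes nothing. All of this stands.

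A reader might infer that the primary comparison is biased towards one arm, or that the trial loses power. The documents support neither: they give no reason to expect unequal loss, and equal loss leaves power near 100%.

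**Conclusion.** The inconsistency is real and concerns the primary outcome. Breaths without valid SpO₂ are excluded, DV is not reduced to match, and applied literally that time belongs to no zone. The percentage shrinks by exactly (1 − m) only if every breath needs SpO₂ and loss is unrelated to zone; otherwise the shrinkage may be smaller or absent. The size cannot be derived from the documents. On assumed equal loss of 5% to 15%, a 14-minute difference would read as 13.3 to 11.9 minutes, with little effect on power. A spurious difference requires unequal loss, and it would favour the arm losing more signal. The silence on whether an excluded breath ends a run matters mainly if loss consists of scattered single breaths. It would be going too far to read this as evidence of how the analysis was actually run: the point is an unreconciled specification that should be settled before the database is locked.

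**What to change.** - **Denominator and numerator.** In the formula, define DV as the summed duration of evaluable breaths in the window. Apply the identical validity condition to T_UZ whatever the other parameters show; otherwise the reversed error in Step 2 appears.
- **Scope.** Use the same base for the secondary zone outcomes, by time and by breath. Put missing or low-quality EtCO₂ under the same condition: it is also a zone parameter, and the Missing data section gives no rule for it.
- **Runs.** Prespecify whether an excluded breath ends a 30-second run. A short maximum gap is one option: excluded breaths within it neither count towards the run nor end it, and a longer gap ends it.
- **Reporting.** Show non-evaluable time by arm for the first three hours beside the primary result. Add a sensitivity analysis, either with total-time DV or with zones defined without SpO₂.

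The cost is SAP wording and a change to the datalogger processing; no new data are needed. Percentages become noisier in patients with little evaluable time. Bias remains if signal is lost more often during desaturation. With a maximum gap, some short episodes cut by longer dropouts are still missed, at worst 7% of the percentage in the simulation with an 8-second maximum (1 − 0.93).

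### The stated sample-size inputs (14.0 min, SD 10.0 min, 5% type I error, 95% power) give about 30 patients before dropout, not 196

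*Combined protocol and SAP*

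**What the plan says.** The Sample size section of the combined protocol and SAP reports a G*Power calculation and concludes: "Based on this analysis the trial was designed to enroll at least 196 patients in total". The target is given as follows: "This number of patients was expected to be sufficient to detect a reduced ventilation time of 14.0 minutes in the unacceptable zone". The variability comes from a cited randomised study of automated ventilation after cardiac surgery: "considering a common standard deviation of 10.0 minutes". The type I error is 5% and the power 95%. The sentence ends with "similar allocation of subjects to each group and corrected for dropouts".

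The section does not give the test, the number of sides, the dropout rate or the number of patients before dropout.

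Three other places bear on the calculation:

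- The Predefined statistical analysis plan section makes all tests two-sided at 5%, does not adjust P-values for multiple comparisons, and assigns a Student's t-test to the primary outcome.
- The Missing data section states: "No or minimal missing for the primary and secondary outcomes are anticipated". The exception is SpO₂ quality, which is handled by excluding breaths.
- The primary outcome is a percentage, not a number of minutes: "Percentage of time (during at least 30 seconds) in the unacceptable zone", over the first three hours or until extubation if that comes earlier.

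**The concern.** A difference of 14.0 minutes against an SD of 10.0 minutes is a very large standardised effect, and detecting it with 95% power takes few patients. A total of 196 is several times too large for it, so the figure and its stated inputs do not belong together.

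What is at stake is the design justification. The trial report would be expected to repeat this paragraph as the basis for the trial's size. A reader could not reproduce it from this document, and could not tell whether the trial was sized for 14 minutes, for something nearer 5 minutes, or for 14 minutes with a much larger SD.

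**Working it through.** **Inputs.** From the Sample size section: difference Δ = 14.0 min, common SD σ = 10.0 min, α = 0.05, power 0.95, 1:1 allocation, stated total 196 (98 per arm). From the analysis section: two-sided t-test. The dropout rate is not stated; 10% and 20% are used below as assumptions.

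**Standardised effect.** d = Δ/σ = 14.0/10.0 = 1.4.

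**Attempt to reproduce 196.** The normal approximation per arm is

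n = 2(z₀.₉₇₅ + z₀.₉₅)²/d² = 2(1.960 + 1.645)²/1.4² = 25.99/1.96 = 13.3,

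so 14 per arm and 28 in total. The exact calculation uses the noncentral t distribution with 2n − 2 degrees of freedom and noncentrality d√(n/2). Because the section names neither the test nor its sides, variants were also run.

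| Test, 95% power | Power at one fewer per arm | Power at n per arm | Total | 10% dropout | 20% dropout |
|---|---|---|---|---|---|
| t, two-sided | 0.946 (14) | 0.959 (15) | 30 | 34 | 38 |
| t, one-sided | 0.936 (11) | 0.953 (12) | 24 | 28 | 30 |
| Rank test, two-sided, minimum asymptotic efficiency 0.864 | 0.943 (16) | 0.955 (17) | 34 | 38 | 44 |

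Dropout is applied as n/(1 − r), rounded up per arm; for example 15/0.90 = 16.7, so 17 per arm and 34 in total. Raising the power of the two-sided t-test to 99% gives only 40 before dropout.

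**Dropout needed to reach 196.** From 30: 1 − 30/196 = 84.7%. From 24: 1 − 24/196 = 87.8%. From 34: 1 − 34/196 = 82.7%. Even a 50% loss takes 30 only to 60.

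**Power at the stated size.** With 98 per arm the noncentrality is 1.4 × √49 = 9.8, and 9.8 − 1.96 = 7.84. The type II error is of the order of 10⁻¹⁵, so power is effectively 100%.

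**What 196 would correspond to** (two-sided 5%, 95% power):

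| Evaluable per arm | d | Difference if SD = 10 | SD if difference = 14 |
|---|---|---|---|
| 98 (no loss) | 0.518 | 5.2 min | 27.1 min |
| 88 (10% loss) | 0.546 | 5.5 min | 25.6 min |
| 78 (20% loss) | 0.581 | 5.8 min | 24.1 min |

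More than one set of inputs gives 196. A two-sided test with d = 0.52 and no dropout gives 196. So does a one-sided test with d = 0.5 and 10% dropout: 176 before loss, and 176/0.90 = 195.6. These show only that 196 does not identify its own inputs; they are not evidence of what was entered.

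**Scale of the outcome.** Over the full 180 minutes, 14.0 min is 14.0/180 = 7.8 percentage points. For a patient ventilated for 120 minutes (an assumed duration) it is 14.0/120 = 11.7 points. For 5.2 min the figures are 2.9 and 4.3 points.

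**The case against.** The arithmetic is not in dispute. The strongest counter-case is about weight and about how dropout is argued.

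First, the Missing data statement concerns outcome measurements, not loss of patients. Randomisation took place right after consent, on the day before surgery. Postoperative ARDS and need for extracorporeal membrane oxygenation are exclusion criteria, and patients who withdrew consent were excluded. Patients could therefore be lost before contributing any ventilation data, and the expectation of little missing data says nothing about that rate. This stands as far as it goes: the statement is weak evidence on dropout, and 10% to 20% is only an assumption. It does not rescue 196. At 30% to 50% loss the two-sided t-test total is 44 to 60 and the rank-test total 50 to 68.

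Second, dividing 196 by 30 (6.5-fold) sets a dropout-corrected figure against an uncorrected one. That is fair. Like for like, with the assumed dropout, the ratio is 196/38 to 196/34, or 5.2 to 5.8.

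Third, enrolment is complete, and on the stated inputs 196 is more than enough, so no decision about size remains. This is right, and it limits the consequence. But the section presents 196 as the result of the calculation at 95% power, not as a generous margin above it.

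Fourth, the cited study and the online protocol were not available for this check. The claim is therefore only that the figure cannot be reproduced from this document.

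**Conclusion.** The concern holds. On the stated inputs the required total is 30 before dropout (24 if one-sided, 34 for a rank test at its worst-case efficiency). With an assumed 10% to 20% dropout none of these exceeds 44, against 196 stated. No dropout rate that the document could support closes the gap, and it describes no multiplicity adjustment, unequal allocation or other feature that would. At least one of the effect, SD, power, sidedness, dropout allowance or rationale for 196 is misreported; the document does not show which.

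The consequence is confined to the design justification. If 14.0 and 10.0 minutes are correct, the trial is larger than needed for that target. If either is wrong, the power for 14 minutes is unknown. In neither case does this discrepancy itself alter the planned t-test, mean difference or confidence interval. It should be corrected before the results are reported.

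**What to change.** Recover the G*Power record and restate what was entered: test, number of sides, effect, SD, power, total before dropout and dropout rate, so that the paragraph reproduces 196.

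If 14.0 and 10.0 minutes were the true inputs, say that they require about 30 patients before dropout. Then give the actual reason for 196, or the difference detectable with 95% power at the evaluable number: about 5.2 minutes at 98 per arm if the SD is 10, and 5.5 to 5.8 minutes with 10% to 20% loss.

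In the same paragraph, express the target on the percentage scale of the primary outcome and state the ventilation duration assumed in the conversion.

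The cost is one corrected paragraph. Enrolment and the analysis are unchanged.
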